4.8.4 Vital Signs and Physical Measurements

Vital signs, body weight, and height will be measured at Screening, Baseline, every visit during the treatment period, early termination, and Follow-up Week 2 for all enrollment groups.

A by-subject listing of vital signs and physical measurements will be provided for screened subjects.

Vital Sign and Physical Measurement Changes From Baseline Over Time

Values and changes from baseline in vital signs and physical measurements will be summarized using descriptive statistics at baseline and each scheduled visit in the on-treatment and follow-up safety analysis periods by enrollment group and overall.

Vital Sign and Physical Measurement Abnormalities

Vital sign and physical measurement abnormalities in safety analysis periods will be summarized by treatment group and overall as the number and percentage of subjects in the following categories:

- Systolic blood pressure (mmHg): < 90, > 140, > 160
- Diastolic blood pressure (mmHg): < 50, > 90, > 100
- Heart rate (bpm): < 60, > 100
- Temperature (C): < 36, > 38
- Respiratory rate (breaths/min): < 12, > 20
- Weight change from baseline: $\leq -7\%$, $\geq 7\%$.

Abnormalities will be summarized on-treatment for treated subjects, and follow-up for follow-up subjects. Subjects have a non-missing measurement in the safety analysis period (plus baseline for weight change) to be included for a given parameter.

4.8.5 *Electrocardiograms*

ECGs will be measured at the following visits: Screening; Baseline; Weeks 4, 24, and 52 for the 52-week PRN (2-8) and (9-14) dosing groups; Weeks 4 and 12 for the 12-week EOD+PRN and PRN (2-8) dosing groups; early termination; Follow-up Week 2.

A by-subject listing of ECG results will be provided for screened subjects.

ECG Interpretation Shifts From Baseline

The shift from baseline to worst on-treatment ECG interpretation will be summarized as the number and percentage of treated subjects with normal, abnormal, and clinically significant abnormal interpretations by enrollment group and overall. Subjects must have a non-missing ECG interpretation at baseline and an on-treatment visit to be included.

ECG Changes From Baseline Over Time

Values and changes from baseline in ECG intervals (e.g., RR, QRS, PR, QT, QTcB, QTcF) and ventricular heart rate will also be summarized using descriptive statistics at baseline and each scheduled visit in the on-treatment and follow-up safety analysis periods by enrollment group and overall.

ECG Abnormalities

ECG abnormalities in safety analysis periods will be summarized by treatment group and overall as the number and percentage of subjects in the following categories:

- QTcB (msec): > 450, > 480, > 500
- QTcF (msec): > 450, > 480, > 500.

Abnormalities will be summarized on-treatment for treated subjects, and follow-up for follow-up subjects. Subjects have a non-missing measurement in the safety analysis period to be included for a given parameter.

ECG abnormalities will be presented together with vital sign and physical measurement abnormalities in the same tables (see Section [4.8.4](#)).

4.9 *Non-Study Medications*

The following non-study medications will be summarized by anatomical therapeutic class (ATC) and preferred name by enrollment group and overall for treated subjects:

- Prior medications, defined as those with an imputed start or stop date < IWRS enrollment date – 14 days.
- Concomitant medications, defined as those with an imputed start or stop date ≥ IWRS enrollment date – 14 days.

- Prophylactic migraine medications taken on or after informed consent and before the start of study drug, defined as those with (1) informed consent date \leq imputed start or stop date $<$ study drug first dose date, or (2) imputed start date \leq informed consent date $<$ study drug first dose date $- 1$ day \leq imputed stop date.
- Prophylactic migraine medications taken on or after the start of study drug, defined as those with an imputed start or stop date on or after the study drug first dose date.*
- Standard of care migraine medications taken on or after informed consent and before the start of study drug.
- Standard of care migraine medications taken on or after the start of study drug.*

Endpoints marked with “*” will also be summarized by subgroup level and overall for key extrinsic exposure factors (see Section 4.2.6).

For each subject, multiple records of the same medication will be counted only once within each ATC and preferred name.

Medications will be presented in descending order of overall frequency within ATC and preferred name.

By-subject listings of non-study medications, non-study prophylactic migraine medications, and non-study standard of care migraine medications will be provided for screened subjects.

Refer to the BHV3000 Core SAP for non-study medication start and stop date imputation, and listing content.

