### 2. Medical History and Concurrent Diseases

- a) Patient history of HIV disease
- b) Patient history with current evidence of uncontrolled, unstable or recently diagnosed cardiovascular disease, such as ischemic heart disease, coronary artery vasospasm, and cerebral ischemia. Patients with myocardial infarction (MI), acute coronary syndrome (ACS), percutaneous coronary intervention (PCI), cardiac surgery, stroke or transient ischemic attack (TIA) during 6 months prior to screening.
- c) Uncontrolled hypertension or uncontrolled diabetes (however, patients can be included who have stable hypertension and /or diabetes for 3 months prior to screening). Blood pressure greater than 150 mm Hg systolic or 100 mm Hg diastolic after 10 minutes of rest is exclusionary.
- d) Patient has a current diagnosis of major depressive disorder or has had a major depressive episode within the last 12 months, other pain syndromes, psychiatric conditions, dementia, or significant neurological disorders (other than migraine) that, in the Investigator's opinion, might interfere with study assessments
- e) Patient has a history of gastric, or small intestinal surgery, or has a disease that causes malabsorption
- f) Patients has a history or diagnosis of Gilbert's Syndrome or any other active hepatic or biliary disorder

- g) The patient has a history or current evidence of any unstable medical conditions (e.g., history of congenital heart disease or arrhythmia, known or suspected infection, hepatitis B or C, or cancer) that, in the investigator's opinion, would expose them to undue risk of a significant adverse event (AE) or interfere with assessments of safety or efficacy during the course of the trial
- h) History of, treatment for, or evidence of, alcohol or drug abuse within the past 12 months or patients who have met DSM-V criteria [15] for any significant substance use disorder within the past 12 months from the date of the screening visit
- i) Patients should be excluded if they have a positive drug screen for drugs of abuse that in the investigator's judgment is medically significant, in that it would impact the safety of the patient or the interpretation of the study results. In addition:

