### 5. ECG and Laboratory Test Findings

- a) Estimated glomerular filtration rate (eGFR) according to the re-expressed abbreviated (four-variable) Modification of Diet in Renal Disease (MDRD) Study equation ≤ 40 ml/min/1.73m
- b) Corrected QT interval > 470 msec (QTc by method of Frederica), at Screening
- c) Left Bundle Branch block
- d) Right Bundle Branch Block with a QRS duration  $\geq 150$  msec.
- e) Intraventricular Conduction Defect with a QRS duration ≥ 150 msec.

- f) Serum bilirubin (Total, Direct or Indirect) bilirubin > 1 x ULN (Only abnormal values of between 1-1.5x ULN may be repeated once for assessment of eligibility during the screening period.)
- g) Neutrophil count  $\leq 1000/\mu L$  (or equivalent).
- h) AST or ALT > 1 x ULN (Only abnormal values of between 1-1.5x ULN may be repeated once for assessment of eligibility during screening period.)
- i) HbA1c > 6.5%

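### The lowest QTcF and blood-pressure abnormality rows lie below the entry limits and take no account of baseline, so they count pre-existing and new values together

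*SAP*

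**What the plan says.** **Abnormality categories.** SAP 4.8.4 lists "Systolic blood pressure (mmHg): < 90, > 140, > 160" and "Diastolic blood pressure (mmHg): < 50, > 90, > 100". SAP 4.8.5 lists "QTcB (msec): > 450, > 480, > 500" and "QTcF (msec): > 450, > 480, > 500".

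**Who is counted.** For the ECG rows the rule is "Subjects have a non-missing measurement in the safety analysis period to be included for a given parameter". For vital signs it is "Subjects have a non-missing measurement in the safety analysis period (plus baseline for weight change) to be included for a given parameter". The tables cover the on-treatment period (treated subjects) and follow-up (follow-up subjects). There is no pre-treatment column.

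**Entry limits.** Protocol 5.3 excludes "Corrected QT interval > 470 msec (QTc by method of Frederica), at Screening" (exclusion 5b) and states "Blood pressure greater than 150 mm Hg systolic or 100 mm Hg diastolic after 10 minutes of rest is exclusionary" (exclusion 2c).

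**Baseline comparisons planned elsewhere.** For vital signs and ECG intervals, SAP 4.8.4 and 4.8.5 plan descriptive changes from baseline by visit. SAP 4.8.5 adds a baseline-to-worst shift of the overall ECG interpretation. By-subject listings are also planned. For laboratory tests, SAP 4.8.3 plans categorical shifts from baseline: low/normal/high, multiples of ULN for ALT and AST, and toxicity grade.

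**The concern.** A table headed as on-treatment abnormalities is read as what happened after dosing started. That reading fails if a patient can enter already above the cut-off and be counted for staying there. A randomised trial has a control arm in which such patients appear too. This study has one treatment and no control (Protocol 9.4), so each patient's own baseline is the main internal reference.

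A row that mixes the two kinds of case can suggest a signal where nothing changed, or hide a modest number of true rises among pre-existing ones. Cardiovascular safety is part of the drug's rationale (Protocol 1.4). The study also admits patients with contraindications to triptans (Protocol 5.2, criterion 2g) and patients with stable hypertension (exclusion 2c). The QTc and pressure tables will therefore be read closely even though they are not primary or secondary endpoints.

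**Working it through.** The documents state no rate or precision for these tables, so there is no plan figure to reproduce. The check compares cut-offs with limits and then reads the counting rule.

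**Step 1. Each upper cut-off against its entry limit.**

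| Parameter | Entry limit | Cut-off | Position |
|---|---|---|---|
| QTcF (msec) | 470, at Screening | 450 | 20 below |
| | | 480 | 10 above |
| | | 500 | 30 above |
| Systolic (mmHg) | 150 | 140 | 10 below |
| | | 160 | 10 above |
| Diastolic (mmHg) | 100 | 90 | 10 below |
| | | 100 | equal |
| QTcB (msec) | none | 450, 480, 500 | no comparison |

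Of the seven upper cut-offs with an entry limit, three lie below it, one equals it and three lie above it. The three below are the lowest tier of each parameter. The eligible bands already above a cut-off are QTcF above 450 up to 470, systolic above 140 up to 150, and diastolic above 90 up to 100.

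**Step 2. The counting rule.** SAP 5.4 starts the on-treatment safety period after the first dose, so the baseline reading itself is not counted. One later reading above the cut-off is enough, whatever the baseline was.

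**Step 3. An unchanged patient.** QTcF is 460 at Screening, Baseline and Week 4. The patient is eligible (460 ≤ 470) and is counted at Week 4 (460 > 450) with a change of 0. A stable 146/94 is eligible (146 ≤ 150, 94 ≤ 100) and is counted in both pressure rows (146 > 140, 94 > 90).

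**Step 4. Illustration of size, on assumptions.** The documents give no QTc or pressure distribution. The figures below come from a simulation with no drug effect, normal between-subject and within-subject variation, and the entry limit applied to one screening reading. All means and SDs are assumed.

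- QTcF: between-subject SD 15, within-subject SD 10, 3 on-treatment ECGs (Weeks 4, 24, 52).
- Systolic: SDs 11 and 8, 13 visits.
- Diastolic: SDs 7 and 6, 13 visits.

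Thirteen is the scheduled maximum in Protocol Table 1 (Week 4 plus 12 later visits). The 12-week group has 3 (Weeks 4, 8, 12).

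| Row | Assumed mean | Above at baseline, per 2000 | Counted on treatment, per 2000 | Both, per 2000 | Both / counted |
|---|---|---|---|---|---|
| QTcF > 450 | 405 | 12.6 | 29.9 | 5.6 | 19% |
| | 415 | 50.5 | 112.5 | 28.3 | 25% |
| | 425 | 157.4 | 313.3 | 107.0 | 34% |
| Systolic > 140 | 115 | 62.0 | 317.3 | 51.0 | 16% |
| | 120 | 126.6 | 555.5 | 110.9 | 20% |
| | 125 | 234.8 | 850.3 | 215.6 | 25% |
| Diastolic > 90 | 74 | 81.0 | 434.9 | 65.8 | 15% |
| | 77 | 152.8 | 687.4 | 133.0 | 19% |
| | 80 | 261.6 | 982.2 | 239.7 | 24% |

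Of those above the cut-off at baseline, the share also counted on treatment was 44% to 68% for QTcF, 82% to 92% for systolic and 81% to 92% for diastolic. In the same runs, subjects both above at baseline and counted on treatment in the next tier numbered at most 0.2 per 2000 for QTcF > 480, 2.5 for systolic > 160 and 16.3 for diastolic > 100.

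**Step 5. What removing pre-existing cases leaves.** For QTcF > 450: 29.9 − 5.6 = 24.3, 112.5 − 28.3 = 84.2 and 313.3 − 107.0 = 206.3 per 2000. Most counted cases remain. They are readings that crossed the cut-off through ordinary variation.

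**The case against.** The strongest reply is that the SAP does use baseline for these parameters. Changes from baseline are summarised at every scheduled visit, and Protocol 9.1 names minimum and maximum among its example statistics, so the largest rise at a visit may be displayed. There is an ECG-interpretation shift with a clinically significant category, by-subject listings for all screened subjects, and an investigator judgement on ECG abnormalities (Protocol 6.2.2). The follow-up rows start more than 7 days after the last dose, so persistent pre-existing values should recur there. These are supportive tables with no test attached, and a shift table could be produced later. This stands as a limit on seriousness. None of these outputs, however, says how many patients crossed a QTc or pressure cut-off for the first time on treatment. Visit summaries are not linked to categories, the ECG shift concerns overall interpretation, and follow-up is a separate count not tied to baseline.

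Four stronger readings are tempting, and the documents do not support them.

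- A reader might infer that every tier is contaminated. Only the lowest tier of three parameters lies below its limit.
- A reader might infer that anyone who entered above a cut-off is counted automatically. A post-dose reading above it is still needed.
- A reader might infer that baseline is ignored altogether. That is true of these abnormality tables only.
- A reader might add that more visits give more chances to exceed a cut-off, which makes the 12-week and 52-week columns hard to compare. That is a different problem. It also affects patients whose usual value is below the cut-off, and a baseline shift table does not remove it.

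Two sources could not be checked. The table templates are in the Mock TLF document (SAP 5.1.1), and the rules for descriptive statistics and counting are in the Core SAP (SAP 4.2.1). SAP 4.8.4 and 4.8.5 do not defer these abnormality tables to the Core SAP.

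**Conclusion.** The point holds for three rows: QTcF above 450 msec, systolic above 140 mmHg and diastolic above 90 mmHg. Each cut-off is below the matching entry limit, the table sets no baseline condition, and a persisting pre-existing value is tabulated as an on-treatment abnormality. The other tiers are largely rather than wholly clear: the QTcF limit applies at Screening only, so a later Baseline ECG could exceed it.

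The size is unknown. The 15% to 34% range in the illustration rests entirely on assumed means and SDs and should not be read as an estimate for this trial. Exclusion of uncontrolled hypertension (5.3, 2c) and of clinically significant abnormalities (5.2, 4a) may make the bands sparser, while admitting stable hypertension may fill them.

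One caveat applies to the limits themselves. SAP 1.1 rests on protocol Version 6. The supplied protocol lacks the cohort on CGRP antagonist biologics that SAP 2.1 attributes to Version 6, so it appears to be an earlier version.

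This is a worthwhile, low-cost improvement to supportive safety tables. It does not touch a primary or secondary endpoint, and no eligibility limit or cut-off has to change.

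**What to change.** In SAP 4.8.4 and 4.8.5, for QTcF, QTcB, systolic and diastolic pressure, do one of the following and keep the present rows:

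- add a table of baseline category by worst on-treatment category, built like the laboratory toxicity-grade shift in SAP 4.8.3; or
- add new-onset rows restricted to subjects at or within the cut-off at baseline, with that number as the denominator.

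If categories of QTcF increase from baseline are wanted as well, the sponsor should define them, because the documents give no thresholds. Confirm the entry limits against protocol Version 6, and check that the Mock TLF does not already contain such a table.

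The cost is a few more table rows. Screening and Baseline values are already collected, so no new data are needed. New-onset rows have somewhat smaller denominators: in the illustration, 0.6% (12.6/2000) to 13.1% (261.6/2000) of subjects would drop out of a row.

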5 CONVENTIONS

5.1 General

5.1.1 *Output Layout*

A list of TLFs and corresponding templates will be presented separately in the Mock TLF document.

Refer to the BHV3000 Core SAP for TLF layout conventions.

5.1.2 *Duplicate Subjects*

If the same subject participates in the study more than once and is assigned more than one subject identifier, then the following conventions will apply to analyses:

- The subject identifier corresponding to the first treatment will be populated across all records in analysis datasets if the subject was treated. Otherwise, the subject identifier corresponding to the first enrollment will be populated if the subject was enrolled but never treated. Otherwise, the subject identifier corresponding to the first screening will be populated if the subject was never enrolled. This will ensure that the output shows unique subjects.
- Pre-treatment parameters (e.g., IWRS screening date, IWRS enrollment date, OP start/end dates, LTT start date, study drug first dose date, enrollment group, demographics, baseline characteristics, medical history, migraine history, cardiac and other risk factors, prior triptan response, current triptan response) will be derived using data only from the subject identifier identified in the previous bullet.
- On-treatment and follow-up parameters (e.g., LTT end date, study drug last/end dates, EOT visit date, last contact date) will be derived using data from all duplicate subject identifiers to ensure that protocol deviations, safety, exposure, migraine, and outcomes research endpoints will be assessed comprehensively.
- Subject disposition will be derived from study exit status data from the last duplicate subject identifier.

5.2 *Subgroups*

5.2.1 *Triptan Non-Responders*

Triptan non-responders are identified using the “Prior Triptan Response” Case Report Form (CRF) pages, which capture reasons for discontinuing triptans taken historically. The definition of triptan non-responder is based on the number of triptans that a subject failed for efficacy reasons. For each triptan and route of administration, the subject is asked the questions shown in [Table 4](#). A subject is considered to have failed a drug for efficacy reasons if they indicated “most or all of the time” for any of the reasons in the table.

A triptan non-responder is defined as any subject that fails two or more molecular entities for efficacy reasons. To be considered a failure for a molecular entity, the subject must have failed on all routes of administration that the subject tried for the molecular entity.

Table 4: Questions Used to Determine Triptan Non-response

	Most or All of the Time	Some of the Time	Rarely	Never
The treatment took too long to relieve my headache pain.				
The pain returned after it was relieved within 24 hours				
The treatment did not relieve my other symptoms (nausea, sensitivity to light or sound, for example).				
I could not count on this treatment to relieve my pain and symptoms every time				

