## 4.3.1 Screening Visit / Observation Period (30 days)

Approximately 2800 patients will be screened to assign up to approximately 2000 patients to rimegepant.

Before any study procedures are performed, patients must sign informed consent. After informed consent, patients will be enrolled in the IWRS system. The patient's migraine history and medical history will be collected at the Screening Visit. All patients will continue to use their migraine prophylactic or standard of care medications during the 30 day observation period. Patients will undergo all screening procedures as detailed in Table 1 and Table 2, after which they will be provided an eDiary to document each day during the 30 day Observation Phase the occurrence and severity of migraines and if the migraine was treated. Patients will also record all migraine standard of care treatments taken during the Observation Phase on a paper diary. After completing the 30 day Observation Phase, patients will return to the clinic, and both their eDiary and paper diary will be reviewed for completeness.

If the patient meets inclusion/exclusion criteria, they may enter the Long Term Treatment Phase.

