#### 6. Other Exclusion Criteria

- a) Prisoners or subjects who are involuntarily incarcerated
- b) Subjects who are compulsorily detained for treatment of either a psychiatric or physical (e.g., infectious disease) illness
- c) Non-compliance with or inability to complete eDiary during Observation Period. Non-compliance is more than 4 missed evening reports during the Observation Period.
- d) Exposure to non-biological investigational agents (other than rimegepant) within the 30 days prior to Screening visit.
- e) Exposure to biological investigational agents within the 90 days prior to Screening visit.
- f) Score of > 0 on the Sheehan Suicidality Tracking Scale (See Section 6.2.5) for the period of 30 days prior to screening.
- g) Previous enrollment in study BHV3000-201.
- h) Participation in any other investigational clinical trial while participating in this clinical trial.

Please see Section 5.4 for Prohibited medications and Section 5.5 for allowable migraine Medications

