Drug accountability is provided by the site on the Drug Accountability CRF.

A by-subject listing will present eDiary exposure (i.e., number of tablets taken) and drug accountability for treated subjects.

Another by-subject listing will present eDiary exposure (i.e., total number of tablets taken) in 4-week intervals during the LTT for treated subjects. This will also display cumulative rimegepant exposure from both sources (i.e., eDiary and drug accountability), and flag subjects with ≥ 10 cumulative tablet difference between the 2 sources.

Another by-subject listing will present batch numbers for treated subjects.

eDiary Exposure

eDiary exposure will be summarized descriptively for treated subjects by enrollment group and overall, and will include the following parameters:

- Time in the OP (weeks), defined as (OP end date – OP start date + 1)/7
- Time from enrollment to last contact (weeks), defined as (last contact date – IWRS enrollment date + 1)/7
- Time in the LTT period (weeks), derived as (LT_T end date – LT_T start date + 1)/7
- Time on rimegepant (weeks), derived as (study drug end dose date – study drug first dose date + 1)/7.*
- Cumulative rimegepant exposure (tablets), derived by summing number of tablets across records with complete dates for subjects who reported taking study medication during the treatment epoch in the eDiary.*
- Average rimegepant exposure (tablets per 4 weeks), derived as 4*cumulative rimegepant exposure/time in the LTT period.*
- Number and percentage of subjects in the average rimegepant exposure (tablets per 4 weeks) categories defined in Section 4.2.6, and also in the following categories:
 - ≥ 12.6 ($\geq 90\%$ compliant with EOD dosing)
 - ≥ 11.2 ($\geq 80\%$ compliant with EOD dosing)
- Number and percentage of subjects who took more than 1 tablet per day on any day. This could be from the same bottle or different bottles due to an unscheduled visit.
- Exposure over time, as defined by the number and percentage of subjects who took
 - ≥ 8 tablets per 4 weeks for 4, 8, 12, 16, 20, ≥ 24 , ≥ 12 , and ≥ 4 weeks. These categories correspond respectively to 1, 2, 3, 4, 5, ≥ 6 , and ≥ 3 4-week intervals that are not necessarily consecutive (see below)
 - ≥ 12 tablets per 4 weeks for 4, 8, 12, 16, 20, ≥ 24 , ≥ 12 , and ≥ 4 weeks
 - ≥ 13 tablets per 4 weeks for 4, 8, 12, 16, 20, ≥ 24 , ≥ 12 , and ≥ 4 weeks

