5.4 Analysis Periods

Analysis periods are defined as follows:

- Observational Period (OP): measurement date/time on or after the OP start date/time through the OP end date/time. This period is used to assess the number of migraine days per 4 weeks during the OP.
- Pre-treatment: measurement date/time on or before the study drug first dose date/time. This period is used to derive baseline values, and to assess safety and outcomes research endpoints.
- Post-enrollment: measurement date/time after the IWRS enrollment date/time through the EOT visit date + 7 days. This period is used to derive analysis visit windows for slotting observations.
- Follow-up: measurement date after the EOT visit date + 7 days. This period is used to slot observations.
- Long-term treatment (LTT): measurement date/time on or after the LTT start date/time through the LTT end date/time. This period is used to assess the number of migraine days per 4 weeks and number of tablets taken during LTT.
- On-treatment safety: measurement date/time after the study drug first dose date/time through the study drug last dose date + 7 days. Note that AEs with imputed start date equal to the study drug first dose date are part of this period (refer to the BHV3000 Core SAP for AE start date imputation). This period is used to assess safety endpoints on treatment.
- Follow-up safety: measurement date after the study drug last dose date + 7 days. This period is used to assess safety endpoints during follow-up.

See Section 5.3 for derived dates for determining analysis periods. If measurement time is missing or not collected, then the measurement date will be compared to the derived date.

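### For a subject dosed in turn under two identifiers, SAP 5.1.2 counts the off-drug interval between the two courses as time on rimegepant

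*SAP*

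**What the plan says.** Protocol 5.3 lists "Previous enrollment in study BHV3000-201" as exclusion 6g. SAP 5.1.2 nevertheless sets conventions that apply "If the same subject participates in the study more than once and is assigned more than one subject identifier":

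- **Anchor.** "The subject identifier corresponding to the first treatment will be populated across all records in analysis datasets if the subject was treated".
- **Starting values.** Enrollment group, IWRS enrollment date, LTT start date and first dose date, among other pre-treatment items, "will be derived using data only from the subject identifier identified in the previous bullet".
- **Ending values.** LTT end, last and end dose dates, end-of-treatment (EOT) visit date and last contact date "will be derived using data from all duplicate subject identifiers". The stated aim is a comprehensive assessment of safety, exposure and outcomes.

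SAP 5.3 defines the end dose date as the latest day on which dosing was reported. SAP 5.4 then defines the on-treatment safety period as "measurement date/time after the study drug first dose date/time through the study drug last dose date + 7 days", and follow-up safety begins only after that. SAP 4.8.1 derives time on rimegepant and patient-years from end dose minus first dose plus one day. Average exposure is "derived as 4*cumulative rimegepant exposure/time in the LTT period". SAP 4.8.2 uses the same first-dose, end-dose and last-dose dates as reference dates for exposure-adjusted adverse events.

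Every entry to LTT is preceded by screening and an Observation Period. During that period, Protocol 4.3.1 says, "All patients will continue to use their migraine prophylactic or standard of care medications during the 30 day observation period". No study drug is dispensed until the Baseline Visit.

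**The concern.** The two ends of the treatment span come from different participations, and no section subtracts what lies between them. For a person who completed one course, stopped, was screened again and started a second course, the interval without drug becomes part of the treatment course.

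Three things follow for that person. Time on rimegepant, LTT time and patient-years are overstated. The tablets-per-4-weeks average is diluted, and the SAP uses that average as a key exposure subgroup and as a split for an eDISH plot. Adverse events and laboratory values from the interval are tabulated as on-treatment. These include the first course's follow-up visit and the second screening and baseline assessments, all recorded while the person had no study drug.

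**Working it through.** The plan gives no figure for this situation, so there is nothing to reproduce. The check applies the SAP's date rules literally.

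**Inputs**
- Course length: 12 weeks = 84 days (every-other-day group), or 52 weeks = 364 days (as-needed groups).
- Tablets at strict every-other-day dosing: 84/2 = 42 per 12-week course, so 84 over two courses.
- Observation Period: 30 days, with a window of 2 days either way in the schedule tables.
- Average-exposure categories (SAP 4.2.6): below 2, 2 to below 8, 8 to below 14, and 14 or more tablets per 4 weeks.
- Every-other-day compliance cut-offs (SAP 4.8.1): 12.6 (90%) and 11.2 (80%).
- **Assumed**, because the documents do not give them: a gap of 28 to 182 days between courses, and 1 to 20 such subjects.

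**Formulas**, with course lengths d1 and d2 and gap g in days
- SAP span = d1 + g + d2; time in dosing courses = d1 + d2.
- Relative overstatement = g / (d1 + d2).
- Average exposure = 4 × tablets / weeks.

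**Two 12-week courses, 84 tablets in total**

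| Gap | SAP span (weeks) | Time in courses (weeks) | SAP average | Average by course |
|---|---|---|---|---|
| 30 days | 198/7 = 28.3 | 24 | 4 × 84/28.3 = 11.9 | 4 × 84/24 = 14.0 |
| 6 weeks | 12 + 6 + 12 = 30 | 24 | 4 × 84/30 = 11.2 | 14.0 |
| 26 weeks | 12 + 26 + 12 = 50 | 24 | 4 × 84/50 = 6.7 | 14.0 |

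Any gap takes this subject out of the 14-or-more category. The 30-day and 6-week gaps lead to the 8-to-below-14 category, and the 26-week gap to the 2-to-below-8 category.

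**Time and patient-years.** With a 30-day gap the SAP gives 198/365.25 = 0.542 patient-years, against 168/365.25 = 0.460 by course, an overstatement of 30/168 = 17.9%. For an 84-day and a 364-day course with the same gap it is 30/448 = 6.7%.

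**Misclassified safety time.** The first 7 days after the first course's last dose would be on-treatment in any case. With a 30-day gap, 30 − 7 = 23 days are wrongly labelled.

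**Visit windows.** Study days run from the first enrollment date. Suppose that dosing starts on the enrollment day in a 12-week group and the gap is 30 days. The second course then starts on day 84 + 30 + 1 = 115, and its Week 2 visit (course day 15) falls on day 129. SAP Table 6 has no post-enrollment window after day 126 for non-questionnaire endpoints. The pooled EOT date also keeps these values out of the follow-up windows.

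**Trial level.** If 1,800 subjects complete 52 weeks and 200 complete 12 weeks, total exposure is (1,800 × 364 + 200 × 84)/365.25 = 1,839.8 patient-years. One subject with a 30-day gap adds 30/365.25/1,839.8 = 0.004%. Twenty subjects with 180-day gaps add 20 × 180/365.25/1,839.8 = 0.54%.

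**The case against.** The strongest reply is that this rarely arises and barely matters. Most of its parts stand.

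- **Not every duplicate has a gap.** SAP 5.1.2 also covers people never treated or never enrolled. If drug was taken under one identifier only, first and end dose lie in the same course. If two participations overlapped, there may be no gap. A reader might infer that every duplicate contributes at least a month off drug. The documents do not support that.
- **Rare liver events.** A reader might also infer that one misattributed case could change the concurrent ALT/AST and bilirubin result. That does not follow. Under Protocol 5.3, AST, ALT or bilirubin above 1 × ULN excludes (values of 1 to 1.5 × ULN may be repeated once), and Protocol 4.3.2 makes dosing wait for baseline results. A validly re-dosed subject cannot have second-screening or baseline values near 3 × ULN for transaminases or 2 × ULN for bilirubin. What remains is mainly the first course's own late liver tests, where an on-treatment label is the conservative choice.
- **Sustained-use subgroups.** Those defined by 14 or more, or 20 or more, tablets per 4 weeks count separate 4-week intervals that need not adjoin. In the example, the first course's three intervals hold 14 tablets each, so the subject stays in the 14-or-more-for-12-weeks subgroup. Cumulative tablets do not change. Migraine-day rates divide by diary days in the treatment epoch and are largely protected.
- **The threshold is delicate anyway.** One missed tablet gives 4 × 83/24 = 13.8 with no gap. A 6-week gap still meets the 11.2 cut-off.
- **Questionnaires and deviations.** The Week 12 questionnaire window in Table 6 is open-ended. SAP 4.4.2 already treats enrollment of ineligible subjects as a significant deviation, tabulated and listed.

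The SAP also subtracts no dose interruptions for anyone. That does not answer this point. Non-dosing days within an as-needed course belong to the regimen. Between courses, unused drug has been returned (Protocol 4.3.3) and the subject is not in treatment.

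**Conclusion.** The point holds, as a minor one. For a person dosed sequentially under two identifiers, the SAP's rules give wrong time on rimegepant, LTT time, patient-years and average exposure. They also label events and laboratory values more than 7 days after the first course as on-treatment. In the worked case the average falls from 14.0 to between 11.9 and 6.7 tablets per 4 weeks for gaps of 30 days to 26 weeks. By-visit tables lose non-questionnaire values after day 126 for someone first enrolled in a 12-week group.

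The documents do not say how many such subjects there are, or whether there are any. Trial-level adverse-event rates would hardly move, and the argument does not extend to the liver endpoints. The gap lengths and numbers of subjects are assumptions. The Core SAP, which holds the exposure-adjusted method, is not available, but this SAP sets the reference dates itself.

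**What to change.** In SAP 5.1.2, keep one record per person under the first enrollment group, so that each person still appears in one column. Then add:

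1. On-treatment safety time is the union, over identifiers, of the intervals from first dose to last dose plus 7 days.
2. Time on rimegepant, LTT time and patient-years are summed over courses, as are the reference times for exposure-adjusted adverse events.
3. Events and laboratory values between courses belong to the follow-up safety period of the preceding course. Simply cutting the interval out would leave them in no period, because follow-up safety now starts only after the final last dose plus 7 days.
4. Second-course events are flagged in the listings when the regimen differs from the first.

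The SAP should also say how second-course visits are slotted when they fall after day 126 in a 12-week group. No change to trial conduct is needed. The cost is a few sentences and a special derivation rule for a few subjects.
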